12.6.3. Safety

ECG Parameters
RR Interval

 IF RR interval (msec) is not provided directly, then RR can be derived as: 
 [1] If QTcB is machine read & QTcF is not provided, then: $RR = \left[\left(\frac{QT}{QTcB} \right)^2 \right] * 1000$ [2] If QTcF is machine read and QTcB is not provided, then: $RR = \left[\left(\frac{QT}{QTcF} \right)^3 \right] * 1000$ If ECGs are manually read, the RR value preceding the measurement QT interval should be a collected value then do not derive.
Corrected QT Intervals

 When not entered directly in the eCRF, corrected QT intervals by Bazett's (QTcB) and Fridericia's (QTcF) formulas will be calculated, in msec, depending on the availability of other measurements. IF RR interval (msec) is provided then missing QTcB and/or QTcF will be derived as: $QTcB = \frac{QT}{\sqrt{\frac{RR}{1000}}} \qquad QTcF = \frac{QT}{\sqrt[3]{\frac{RR}{1000}}}$

Clinical Efficacy

- 3-domain Mayo Score: the total score of the 3 domain subscores: [CCI] and [CCI]
- Mayo Clinical Response: ≥3 points or ≥30% improvement from baseline in total Mayo score, along with a decrease in the [CCI] subscore of ≥1 point.
 - i.e., $(\frac{C}{A}) < \text{change from baseline in total mayo score} \leq \frac{CC}{A}$ OR % change from baseline in total mayo score $\leq \frac{CCI}{A}$ AND change from baseline in [CCI] subscore $\leq \frac{C}{A}$.
- 3-domain Mayo Clinical Response: ≥2 points or ≥30% improvement from baseline in partial Mayo score, along with a decrease in the [CCI] subscore of ≥1 point or a [CCI] subscore of [C] or [C].
 - i.e., $(\frac{C}{A}) < \text{change from baseline in partial mayo score} \leq \frac{CC}{A}$ OR % change from baseline in partial mayo score $\leq \frac{CCI}{A}$ AND (change from baseline in [CCI] subscore $\leq \frac{C}{A}$ OR [CCI] subscore of [C] or [C]).
- Mayo Clinical Remission: Total Mayo score of 2 points or lower, with no individual subscore exceeding 1 point.
 - i.e., $\frac{C}{A} \leq \text{total mayo score} \leq \frac{C}{A}$ AND [CCI] subscore = [C] or [C] AND [CCI] subscore = [C] or [C] AND [CCI] subscore = [C] or [C].
- 3-domain Mayo Clinical Remission: At least one point decrease in [CCI] subscore from Baseline to achieve a [CCI] subscore of [C] or [C] and [CCI] subscore = [C] and [CCI] subscore of [C] or [C].
 - i.e. $(\frac{CCI}{A}) \text{ subscore } \frac{C}{A} \text{ or } \frac{C}{A}$ AND change from baseline in [CCI] subscore $\leq \frac{C}{A}$ AND [CCI] subscore of [C] AND [CCI] subscore = [C] or [C].

Clinical Efficacy

UCEIS

The UCEIS is used as an additional tool to assess disease activity based on endoscopic [CCI] and [CCI]. The following table describes how the UCEIS is scored:

Descriptor (score most severe lesions)	Likert scale anchor points	Definition
CCI - This section contained Clinical Outcome Assessment data collection questionnaires or indices, which are protected by third party copyright laws and therefore have been excluded.		

Clinical Efficacy

CCI - This section contained Clinical Outcome Assessment data collection questionnaires or indices, which are protected by third party copyright laws and therefore have been excluded.

The following endpoint for the UCEIS is to be considered at each visit:

- UCEIS Total Score: Sum of all likert scale anchor points scores.
- UCEIS Remission: Participants with a score of 0 or 1 on the UCEIS Total Score.

Geboes

The Geboes Index is divided in 6 grades: architectural changes [grade 0], chronic inflammatory infiltrate [grade 1], lamina propria neutrophils and eosinophils [grade 2], neutrophils in epithelium [grade 3], crypt destruction [grade 4] and erosions or ulcerations [grade 5], and each grade of the score is divided in 4 or 5 subcategories.

Grade		Subgrade	
0	Structural (architectural change)	0.0	No abnormality
		0.1	Mild abnormality
		0.2	Mild or moderate diffuse or multifocal abnormalities
		0.3	Severe diffuse or multifocal abnormalities
1	Chronic inflammatory infiltrate	1.0	No increase
		1.1	Mild but unequivocal increase
		1.2	Moderate increase
		1.3	Marked increase
2	Lamina propria eosinophils and neutrophils (to be graded separately)	2.0	No increase
		2.1	Mild but unequivocal increase
		2.2	Moderate increase
		2.3	Marked increase
3	Neutrophils in epithelium	3.0	None
		3.1	<5% crypts involved
		3.2	=<50% crypts involved
		3.3	>=50% crypts involved
4	Crypt destruction	4.0	None
		4.1	Probable – local excess of neutrophils in part of crypt

Clinical Efficacy

5	Erosion or ulcerative	4.2	Probable – marked attenuation
		4.3	Unequivocal crypt destruction
		5.0	No erosion, ulceration, or granulation tissue
		5.1	Recovering epithelium plus adjacent inflammation
		5.2	Probable erosion – focally stripped
		5.3	Unequivocal erosion
		5.4	Ulcer or granulation tissue

The following endpoint for the Geboes is to be considered at each relevant visit:

- Geboes Index Total Score: Sum of the all the subgrades (i.e. Structural (architectural change) = 0.2 is a score of 2, Chronic inflammatory infiltrate = 1.1 is scored as a 1 etc.).
-

Robarts Histology Index (RHI)

The RHI will be provided by Robarts as an additional tool to measure histologic disease activity.

The RHI Score is a continuous score, ranging from 0-33 with higher scores indicating more severe disease.

For the frequency table of RHI Score the following cut-points will be used:

- Remission: Score <=6,
- Low: Scores >6-<12,
- Moderate/Severe Score: > = 12

Modified Riley Scale

The Modified Riley Scale (MRS) is a 4-point scale (none, mild, moderate and severe) which scores histologic activity based on localization and quantification of neutrophils in the mucosa. A single modified riley scale score is collected at each relevant visit.

Activity	Histological Characteristics	
None	0	Normal biopsy or inactive colitis
Mild	1	Lamina propria neutrophils only = Scattered individual neutrophils
	2	Lamina propria neutrophils only = Patchy collections of neutrophils
	3	Lamina propria neutrophils only = Diffuse neutrophils infiltrate
Moderate	4	Cryptitis/crypt abscesses = <25% crypts involved
	5	Cryptitis/crypt abscesses = 25%- 74% crypts involved
	6	Cryptitis/crypt abscesses = >=75% crypts involved
Severe	7	Erosion or ulceration = Present

Clinical Efficacy
Faecal Calprotectin (FCP)

FCP, a protein biomarker, is measured from the faecal samples. The raw FCP data is highly variable and therefore data should be log-transformed before a change from baseline is calculated.
 
For the frequency table of FCP categories the following cut-points will be used:
 
 • <250, • >= 250 and • >=1000.
C-Reactive Protein (CRP)

CRP will be provided as a clinical chemistry parameter in the Clinical Laboratory dataset.

Inflammatory Bowel Disease Questionnaire (IBDQ)

The IBDQ is a 32-item Inflammatory Bowel Disease-specific health related quality of life instrument evaluating general activities of daily living, intestinal function, social performance, personal interactions, and emotional status. Each item is presented on seven-point scale with higher representing better functioning.
 
The IBDQ items are grouped into four domains with a total score for each being calculated as follows:
 
 • Bowel symptoms (10 items): Sum items 1, 5, 9, 13, 17, 20, 22, 24, 26, 29 • Systemic Symptoms (5 items): Sum items 2, 6, 10, 14, 18. • Emotional Function (12 items): Sum items 3, 7, 11, 15, 19, 21, 23, 25, 27, 30, 31, 32 • Social Function (5 items): Sum items 4, 8, 12, 16 and 28 
The IBDQ Total Score is calculated as follows:
 
 • IBDQ Total Score: Sum of all 32-items.
Subject Symptom Diary Cards

Participants will be given a diary card at each visit. The number of stools, stool frequency score and rectal Bleeding Score will be transcribed into the eCRF for the 5 days prior to the following visits: Screening, Day 15, Day 29, Day 43, Day 85 and EW.
 
The stool frequency score is on a 4-point scale as follows:
 
 • 0 = Normal • 1 = 1-2 stools/day more than normal • 2 = 3-4 stools/day more than normal • 3 = >=4 stools/day more than normal 
The rectal bleeding score is on a 4-point scale as follows:
 
 • 0 = No blood seen • 1 = Streaks of blood with stool less than half the time • 2 = Obvious blood with stool most of the time

Clinical Efficacy

 • 3 = Blood alone passed. 
The average score and maximum score be considered for both stool frequency and rectal bleeding over the 5 days prior to at each visit:
 
 • Average Score: [Sum of scores over 5 prior days] / [number of prior days with a score available] • Maximum Score: Maximum (i.e. highest) score collected over 5 prior days. 
The average score will be considered for number of stools over the 5 days prior to at each visit:
 
 • Average Score: [Sum of number of stools over 5 prior days] / [number of prior days with a stool data available]

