5.2. Baseline Definitions

For all endpoints (except as noted in baseline definitions) the baseline value will be the latest pre-dose assessment. Triplicate assessments at a timepoint will be averaged. An additional period baseline will be determined for vital signs, ECGs and clinical labs.

Unless otherwise stated, if baseline data is missing, no derivation will be performed and baseline will be set to missing.

For tables summarising from Day 43 (Part B), all data recorded on day 43 will be used as baseline and if this result is missing then there is no part B baseline.

Parameter	Study Assessments Considered as Baseline				Baseline Used in Data Display	Period Baseline Used in Data Display
	Screening (-30)	Screening (-7 to 30)	Day 1 (Pre-Dose)	Day 1		
Primary: Safety						
Vital Signs ^[1,2]	X		X		Day 1 (Pre-Dose)	Day 43
12-Lead ECG ^[2]	X ^[3]		X		Screening or Day 1 (Pre-Dose)	Day 43
Clinical Laboratory Values including CRP ^[2,4]	X		X		Day 1 (Pre-Dose)	Day 43

Parameter	Study Assessments Considered as Baseline				Baseline Used in Data Display	Period Baseline Used in Data Display
	Screening (-30)	Screening (-7 to 30)	Day 1 (Pre-Dose)	Day 1		
Columbia Suicide Severity Rating Scale (C-SSRS)	X		X		Day 1 (Pre-Dose)	
Secondary						
Mayo Score ^[5]	X				Screening	
UCEIS	X				Screening	
Modified Riley	X				Screening	
Geboes Index	X				Screening	
RHI	X				Screening	
FCP	X		X		Screening	
Exploratory						
Blood Sample: PK				X	Day 1	
Blood Sample: Exploratory Biomarkers, Target Engagement and mRNA Expression			X		Day 1 (Pre-Dose)	
Biopsy Tissue: PK, Inflammatory Biomarkers, mRNA Expression, Target Engagement and Pathway Marker	X				Screening	
IBDQ			X		Day 1 (Pre-Dose)	

NOTES:

- Unless otherwise stated, the mean of replicate assessments at any given time point will be used as the value for that time point.
 - 1: Vital sign measurements include Blood Pressure, Heart Rate, Respiratory Rate, and Body Temperature.
 - 2: Where both screening and pre-dose are available, the value closest to first dose will be used.
 - 3: ECG recordings will be performed in triplicate at screening. The mean of the triplicate measurements should be used.
 - 4: Clinical Laboratory measurements include Clinical Chemistry (which includes CRP), Haematology and Urinalysis.
 - 5: Includes Total Mayo, Partial Mayo and 3-domain Mayo Scores.

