8.1.2.1. Statistical Methodology Specification

8.1.2.1.1 Continuous Endpoints

Secondary and Exploratory Endpoint(s)

 • Change from baseline in Total and 3-domain Mayo Score at Day 43 pre-dose and Day 85. • Change from baseline in Partial Mayo Score at Day 15, Day 29, Day 43 pre-dose and Day 85. • Change from baseline in UCEIS Total Score at Day 43 pre-dose and Day 85. • Change from baseline Modified Riley Scale at Day 43 pre-dose and Day 85. • Change from baseline Geboes Index Total Score at Day 43 pre-dose and Day 85. • Change from baseline RHI Score at Day 43 pre-dose and Day 85. • Change from baseline in CRP at Day 43 pre-dose and Day 85. • Change from baseline in Log-transformed FCP at Day 15, Day 29, Day 43, Day 57, Day 71 and Day 85. • Change from baseline in IBDQ Total Score at Day 43 pre-dose and Day 85.

Model Specification

 Continuous endpoints will be statistically analyzed using a Mixed Models Repeated Measures (MMRM) approach. Terms fitted in the MMRM model will include: 
 Fixed Category : Treatment, Day, Treatment*Day Fixed Continuous Covariates : Baseline Score, baseline*Day Repeated Effect : Day The Kenward and Roger method for approximating the denominator degrees of freedom and correcting for bias in the estimated variance-covariance of the fixed effects will be used. An unstructured covariance structure for the R matrix will be used by specifying 'type=UN' on the REPEATED line with a subject=SUBJID option. 
 In the event that this model fails to converge, alternative correlation structures may be considered such as CS or AR(1). Akaike's Information Criteria (AIC) will be used to assist with the selection of covariance structure. Other covariates maybe explored, if deemed appropriate for sensitivity analyses.
Model Checking & Diagnostics

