12.2. Appendix 2: Schedule of Activities

12.2.1. Protocol Defined Schedule of Events

Procedures	Screening (-30)	Screening (-7 to -30)	Treatment Period ¹⁸													Early Withdrawal ¹⁹	Follow Up (±3) ²⁰
			PART A							PART B							
			Day 1	Day 8 (±3)	Day 15 (±3)	Day 22 (±3)	Day 29 (±3)	Day 36 (±3)	Day 43 (±3) (week 6)	Day 50 (±3)	Day 57 (±3)	Day 64 (±3)	Day 71 (±3)	Day 78 (±3)	Day 85 (+2) (week 12)		
Site Visit	X	X	X		X		X		X		X		X		X	X	X
Phone call				X		X		X		X		X		X			
General/Safety Assessments and Procedures																	
Informed Consent	X																
Subject Demography	X																
Full medical history ¹	X																
Inclusion/Exclusion Criteria	X																
Full physical exam ²	X													X	X	X	
Brief physical exam			X ⁴		X		X		X ⁴		X		X				
Vital signs (BP, HR, RR, temperature)	X		X ⁴		X		X		X ⁴		X		X		X	X	X
12-lead ECG ³	X		X ⁴		X		X		X ⁴		X		X		X	X	X
Concomitant medication review & AE reporting/SAEs ⁵			X-----														
PROs/Questionnaires/Disease Assessments and Procedures																	
Columbia Suicide Severity Rating	X		X ⁴						X ⁴						X	X	

Procedures	Screening (-30)	Screening (-7 to -30)	Treatment Period ¹⁸													Early Withdrawal ¹⁹	Follow Up (±3) ²⁰
			PART A						PART B								
			Day 1	Day 8 (±3)	Day 15 (±3)	Day 22 (±3)	Day 29 (±3)	Day 36 (±3)	Day 43 (±3) (week 6)	Day 50 (±3)	Day 57 (±3)	Day 64 (±3)	Day 71 (±3)	Day 78 (±3)	Day 85 (+2) (week 12)		
Scale (C-SSRS)																	
IBDQ ⁶			X ⁴							X ⁴						X	X
UCEIS, Modified Riley, Geboes Index	X-----X ⁷									X ⁴						X	X
Mayo Score (including sigmoidoscopy and biopsy)	X-----X ⁷									X ^{4, 8}						X	X ⁹
Partial Mayo Score	X-----X ⁷				X		X			X ⁴						X	X
Study Treatment																	
Randomisation			X														
Study medication (three times daily) ¹⁰			X-----XX-----X ¹¹														
Dispensing of study medication			X		X					X							
Dispensing of diary cards			X		X		X			X		X		X			
Collection of diary cards					X		X			X		X		X		X	
Laboratory (Safety) Assessments and Procedures																	
TB, HIV, Hep B, Hep C Ab, C. Difficile toxin	X																
FSH & estradiol (if applicable)	X																
Serum pregnancy test (WCBP only)	X																

Procedures	Screening (-30)	Screening (-7 to -30)	Treatment Period ¹⁸												Early Withdrawal ¹⁹	Follow Up (±3) ²⁰	
			PART A						PART B								

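### SAP Section 12.6.4 computes the 3-domain Mayo Clinical Response on the partial Mayo score, which the SAP elsewhere treats as a different score

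*SAP*

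**What the plan says.** The Clinical Efficacy derivations in Appendix 6 (Section 12.6.4) first define the score: "3-domain Mayo Score: the total score of the 3 domain subscores", with the domain names redacted. The response definition in the same list reads "3-domain Mayo Clinical Response: ≥2 points or ≥30% improvement from baseline in partial Mayo score". It adds a condition on redacted subscores, so that the full criterion asks for an "improvement from baseline in partial Mayo score, along with a decrease in the" value of a redacted subscore, or a qualifying value of a redacted subscore. The programmed rule underneath uses "change from baseline in partial mayo score" for the points criterion and the partial score again for the percentage criterion.

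Elsewhere the two scores are kept apart. Note 5 to the baseline table in Section 5.2 says of the Mayo entry: "Includes Total Mayo, Partial Mayo and 3-domain Mayo Scores". Table 6, the nine-panel plot in Section 8.2.1 and the PK/PD list in Section 9.3 also name them separately. Section 8.1.2.1.1 gives them different visits: "Change from baseline in Total and 3-domain Mayo Score at Day 43 pre-dose and Day 85", but "Change from baseline in Partial Mayo Score at Day 15, Day 29, Day 43 pre-dose and Day 85".

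**The concern.** A response endpoint should be computed on the score in its name, unless the plan says otherwise and gives a reason. Here the name points to one score and the rule to another, with no explanation. A programmer following Section 12.6.4 literally would use the partial score. A reader of the tables would assume the 3-domain score.

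The label is widely used. It appears in the frequency tables (2.10, 2.12, 2.14) and the conditional GEE tables (2.11, 2.13, 2.15) for the Safety, Per Protocol and PP + Completers populations. It also appears in figures such as 2.4 and 2.5 and in Listings 47 and 60 to 62. In arms this small, a few changed classifications would be visible in the reported rates.

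**Working it through.** The plan gives no figure to reproduce, so the main check is textual.

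**1. Is it one slip or consistent?** The partial score appears in the prose and in both criteria of the programmed rule. It is not a single mistyped word.

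**2. Does the neighbouring definition behave the same way?** No. Mayo Clinical Response, in the same list, uses the total Mayo score, which is the score its name implies.

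**3. Are the two scores the same thing under two names?** The SAP does not treat them so. They are listed separately in Sections 5.2, 8.1 (Table 6), 8.2.1 and 9.3. The 3-domain score is analysed at Days 43 and 85 only, with the Total score. The partial score is also analysed at Days 15 and 29. In the schedule (Section 12.2.1), the row that begins "Mayo Score (including sigmoidoscopy and biopsy" has no entry at Days 15 and 29, whereas Partial Mayo has its own row with entries on both days. This pattern suggests that the 3-domain score contains endoscopy and the partial score does not. It is an inference, because the component names are redacted.

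**4. Can the choice of score change a classification?** An illustration needs assumptions:
- each subscore runs 0 to 3;
- the scores share two items and differ in the third (a non-endoscopic item in the partial score, endoscopy in the 3-domain score);
- the subscore condition is a fall of at least 1 point in one shared item, or a value of 0 or 1 on it.

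Suppose the shared items go 2 to 2 and 2 to 1, the non-endoscopic item 2 to 1, and endoscopy stays at 3.
- Partial: 2+2+2 = 6 to 2+1+1 = 4; change −2, −2/6 = −33%. Responder.
- 3-domain: 2+2+3 = 7 to 2+1+3 = 6; change −1, −1/7 = −14%. Not a responder.

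The reverse also occurs. Keep the shared items as above, hold the non-endoscopic item at 2 and let endoscopy go 3 to 2.
- Partial: 6 to 2+1+2 = 5; change −1, −1/6 = −17%. Not a responder.
- 3-domain: 7 to 2+1+2 = 5; change −2. Responder on points.

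A full enumeration added three restrictions at baseline: endoscopy 2 or 3, the item in the subscore condition at least 1, and a four-item sum of 6 to 12. It gave 20,992 equally weighted patterns. Of these, 969 were responders on the partial score only and 2,837 on the 3-domain score only: (969 + 2,837)/20,992 = 3,806/20,992 = 18.1%. These are shares of possible patterns, not of expected patients. They show only that the two rules are not interchangeable under these assumptions.

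**5. What does one reclassified participant weigh?** About 36 participants at 2:1 gives 24 active and 12 placebo.
- Placebo: 1/12 = 8.3 percentage points.
- Active: 1/24 = 4.2 percentage points.

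Section 8.1.2.1.2 runs the GEE only if a group reaches a 30% response at Day 85. One participant can decide that: 7/24 = 29.2% against 8/24 = 33.3%, or 3/12 = 25.0% against 4/12 = 33.3%.

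**The case against.** The strongest reply is that this is loose terminology. Table 1 in Section 2.1 uses the hybrid term *3-domain partial Mayo*, so the authors may have written partial while meaning the 3-domain score. That is plausible and cannot be excluded. It does not remove the problem, because the programmed rule names the partial score and would be coded as such.

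Other limits stand. The endpoint is not primary: the primary objective is safety, and the SAP added this endpoint to what the protocol specified. The GEE is conditional, though the frequency tables are not.

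A reader might also infer more than the documents support:

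- *That Table 1 contradicts Section 12.6.4.* It does not. Table 1 names the endpoint but gives no scoring rule.
- *That the 3-domain score is shown to include endoscopy.* The visit pattern points that way, but the components are redacted.
- *That the fault lies in allowing response without endoscopic improvement.* The fix would not prevent that. Under the assumptions above, a 3-domain score could fall from 8 to 6 with endoscopy unchanged and still meet the 2-point criterion.
- *That endoscopic improvement counts for nothing.* At most this applies to the points and percentage criteria, and only if the inference about endoscopy is right. The other condition rests on redacted subscores.
- *That 3-domain Mayo Clinical Remission is affected.* It is built from individual subscores, so this definition does not touch it.

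**Conclusion.** The point holds as a mismatch between an endpoint's name and its rule. It lies in readable text and is not produced by the redactions. The 3-domain response is defined on the partial Mayo score in both prose and programmed rule, while the rest of the SAP treats that as a separate score with its own visits. Outputs carrying the label would report a different quantity from the one named.

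The effect on results cannot be quantified from the document. What can be stated is the weight of one participant (8.3 points on placebo, 4.2 on active, assuming 12 and 24 analysed) and that the two rules can disagree in either direction if the scores differ by one item. The consequence is for interpreting a non-primary efficacy endpoint. It does not affect the primary safety objective. The document does not show which score the authors intended.

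**What to change.** Before final unblinding:

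1. In Section 12.6.4, name the 3-domain Mayo score in the prose and in both criteria of the programmed rule for 3-domain Mayo Clinical Response.
2. Confirm that the 2-point and 30% thresholds are meant for that score. They currently stand against the partial score and should not be carried over unexamined.
3. If the partial score was intended, keep the rule and rename the endpoint as a partial Mayo response in Table 1, Section 8.1 and all displays.
4. Use one label throughout, and replace *3-domain partial Mayo* in Table 1 accordingly.
5. Tables 2.10 to 2.15 are deliverables at the interim as well as the final analysis. If interim versions exist, record which score they used.

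The cost is SAP wording, one derived variable and, under option 3, display titles. No new data are needed.

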12.6.5. Biomarker

TEAR

Target Engagement
 
 • Ratio = free / total • Target Engagement = $100 - (\text{ratio}_{\text{post}} / \text{ratio}_{\text{baseline}}) * 100$ • BIOMARK dataset: BICAT = TRIPK1 (total) or FRIPK1 (free) and BITESTCD = CONC

12.7. Appendix 7: Reporting Standards for Missing Data

12.7.1. Premature Withdrawals

Element	Reporting Detail
General	
 Participant study completion was defined as one who has completed all phases of the study including the follow-up visit. Withdrawn participants may be replaced in the study at the discretion of the investigator. All available data from participants who were withdrawn from the study will be listed and all available planned data will be included in summary tables and figures, unless otherwise specified.

